## **9. EFFICACY**

### **9.1. General**

#### **9.1.1. Reporting Statistics**

Nominal p-values will be provided for all efficacy analyses in which differences between groups and 95% CIs are evaluated.

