### 9.3.2.2.1. Data Handling

For the purpose of the analysis the influence of ICEs and the presence of the missing data on the estimation of change from baseline to Month 7 PRO means will be taken into consideration. The ICEs are defined as post-randomization events leading to early ALIS/ELC therapy termination due to death, ALIS/ELC-related TEAE, use of rescue medication, or lack of efficacy.

Change from baseline to Month 7 will incorporate the following considerations:

1. A subject who dies after randomization will be assigned the worst observed change score in the entire sample as the change from baseline to Month 7
2. Retrieved Month 7 assessments will be used in the analysis, ie, collected after early termination of ALIS/ELC (see [Section 7.4](#) for definition)
3. Data for subjects who complete 6 months of the randomized treatment however their Month 7 PRO is not available will be imputed based on the observed status distribution from the subjects who completed 6 months of randomized treatment (ALIS/ELC, AZI and ETH), have Month 7 available, and were randomized to the same treatment group. This approach is consistent with MAR approach.
4. When retrieved assessments are unavailable the missing change from baseline to Month 7 will be imputed as follows:
  - For subjects experiencing ICEs other than death, their missing Month 7 PRO will be imputed based on the retrieved assessment distribution from those retrievers who experienced ICE and are exposed to an altered treatment regimen after their ICEs. MNAR imputation of the data for those subjects experiencing ICE is applied.

Justification for usage of retrievers' data is included in [Section 9.3.1.2.1](#).

- For subjects not experiencing ICE, their missing Month 7 PRO data will be imputed based on the observed data distribution from the subjects who completed 6 months of randomized therapy (ALIS/ELC, AZI and ETH), have Month 7 PRO data assessment available, and are randomized to the same treatment group. This approach is consistent with Missing-at-Random (MAR) approach.

Imputation details are included in [Appendix I](#).

The ELC treatment group will be used instead if the ICE retriever subgroup is too small to allow imputations as described above. The decision as to which group will be used in the imputation will be determined prior to unblinding at the data review meeting.

The results of the analyses for each imputation will be combined using Rubin's rule.

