### 10.3. Subjects meeting WSMC

#### 10.3.1. Variable Description

Within-subject meaningful change (WSMC) from baseline to Month 7 is one threshold on the QOL-B Respiratory Symptoms Domain Score and one threshold on the PROMIS

Fatigue Score and their estimation is described in the VAP. The thresholds will be provided after unblinding of the study and will be provided exclusively for the revised scales, therefore this analysis will be included in the CSR appendix.

The WSMC threshold values will be used to categorize subjects into two categories at Month 7: subjects meeting the criteria of change from baseline to Month 7 meeting or exceeding (in the improved direction) the threshold or not.

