### 10.3.2. Analysis

**Endpoint:** Proportion of subjects meeting the within-subject meaningful change threshold as reflected in PRO changes scores in patient-reported symptoms (as assessed by QOL-B Respiratory Symptoms domain and PROMIS F-SF 7a)

**Timepoint:** Change between baseline and Month 7

**Type of endpoint:** Categorical

Summaries will include:

1. Basic summary statistics: number of subjects in each category
2. Difference of proportions (ALIS + background regimen – ELC + background regimen)

Estimation of proportions and differences of proportions together with corresponding 95% CIs will utilize SLR of the proportions adjusted for stratification variable (history of MAC lung infection, initial or subsequent)

The estimation obtained from SLR will be based on the standardized procedure described in [Steingrimsdottir et al\[13\]](#), the SAS macro %Margin, version 2.0 (or later), provided SAS Institute (see SAS note <https://support.sas.com/kb/37/228.html>) will be used for implementation.

Basic summaries will be performed on the observed data (including retrieved data after ALIS/ELC discontinuation), while inferential summaries (SLR) on the imputed. Specifically, for subjects with imputed QOL-B Respiratory Symptoms score data, change from baseline values will be averaged across 50 available imputations. For PROMIS Fatigue, additionally, averaged values will be rounded to the nearest integer. This method will ensure consistency between data usage in this and anchor-based analysis.

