#### Categorical Analysis

The following categories for change from baseline will be defined:

- Very much better if change from baseline = -4
- Much better if change from baseline = -3
- Better if change from baseline = -2
- Somewhat better if change from baseline = -1
- No changed if change from baseline = 0
- Somewhat worse if change from baseline = 1
- Worse if change from baseline = 2
- Much worse if change from baseline = 3
- Very much worse if change from baseline = 4

In addition, the following simplified categories for change from baseline will be defined:

- Improved (Very much better / Much better / Better / Somewhat better) if change from baseline  $\leq -1$
- No change if change from baseline = 0
- Worse (Very much worse / Much worse / Worse / Somewhat worse) if change from baseline  $\geq 1$

Within-subject change from baseline to Month 7 are summarized as follows:

- Proportion of subjects in each PGI-S category for change from baseline to Month 7.
- Proportion of subjects in each PGI-S simplified category (Improved/No change/Worsen) for change from baseline to Month 7 ( $\leq -1$ , 0,  $\geq 1$ ) by treatment group and pooled.
- Between treatment groups comparison of the proportion of subjects in PGI-S Improved simplified category (i.e., change from baseline to Month 7  $\leq -1$ ) using Cochran-Mantel-Haenszel test stratified by history of MAC lung infection (initial or subsequent).

For the purpose of this analysis, PRO data for subjects with missing data, imputations of change from baseline values will be averaged across 50 available imputations and rounded to the nearest integer to obtain a single value per subject.

### 11.3. Culture Conversion by Month 7

The endpoint of interest is the proportion of subjects achieving culture conversion by Month 7. The reporting will be presented based on the ITT analysis set and will be provided by randomized treatment group.

Converters by Month 7 are subjects who have a negative culture at Month 7, and have achieved culture conversion by one of the following:

- MAC culture negative at Month 6 after adjustment for non-productive sputum, or
- Missing MAC culture at Month 6, and one of the below:
  - Achieved culture conversion (2 consecutive monthly negative sputum cultures), have negative culture after conversion, do not have recurrence after conversion, with at most 1 missing sputum assessment at or before Month 5, or
  - Negative culture at Month 5

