#### Imputations for subjects who experienced ICE (other than death) and whose retrieved assessments at Month 7 are unavailable

For subjects experiencing ICEs other than death, their missing change from baseline to Month 7 PRO will be imputed based on the retrieved assessment distribution (flagged as Ref\_MNAR) from those retrievers who experienced ICE and are exposed to an altered treatment regimen after their ICEs. This approach is consistent with MNAR approach.

The missing data will be multiply imputed using PROC MI in SAS. The Sponsor believes that multiple imputation method is appropriate to appropriately estimate the mean and variance of the treatment effect. Fifty replications are sufficient to reflect variability of the imputations. The variables used in the MI model (predictors) will be randomization stratum (history of MAC lung infection, initial or subsequent), PRO score at baseline, and randomized treatment group. [REDACTED]

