The missing data will be multiply imputed using PROC MI in SAS. Fifty replications are sufficient to reflect variability of the imputations. Logistic regression will be used in the MI procedure with model factors including randomization stratum (history of MAC lung infection, initial or subsequent) and randomized treatment group.

[REDACTED]

Imputations for subjects whose Month 6 conversion status is unavailable and who discontinued ALIS/ELC early due to a non-ICE event:

For subjects not experiencing ICE, their missing Month 6 conversion status will be imputed based on the observed data distribution (flagged as Ref\_MAR) from the subjects who completed 6 months of randomized therapy, have Month 6 conversion status available, and are randomized to the same treatment group. This approach is consistent with MAR approach.

The missing data will be multiply imputed using PROC MI in SAS. Fifty replications are sufficient to reflect variability of the imputations. Logistic regression

will be used in the MI procedure with model factor randomization stratum (history of MAC lung infection, initial or subsequent).

Imputations for subjects completing randomized therapy and whose conversion status at Month 6 is unavailable

Data for subjects who complete 6 months of the randomized treatment however Month 6 conversion status is not available will be imputed based on the observed distribution from the subjects who completed 6 months of randomized treatment, have Month 6 conversion status available, and were randomized to the same treatment group. This approach is consistent with MAR approach imputation. The missing data will be multiply imputed using PROC MI in SAS as described above.

Analysis methods

Following each round of imputation, a full set of subject's conversion status at Month 6 will be created by combining the observed values and sets of imputed values under the MNAR and MAR assumptions. This process will result in a total of 50 full sets.

The analysis as specified in Section 9.3.1.2 will be performed using each of the 50 full sets. The 50 sets of results will be then combined using Rubin's rule implemented via SAS PROC MIANALYZE with the specification of their effect estimates together with the corresponding standard errors, resulting in a single set of estimates and testing statistics for the treatment effect.

Imputation of conversion status by Month 7

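### Averaging the 50 imputations before classifying responders makes the WSMC 95% CI too narrow and can bias the arm difference; the same rule makes the PGI-S test reject too often under no effect

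*SAP*

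**What the plan says.** SAP 10.3.1 splits subjects into those who do and do not reach a WSMC threshold at Month 7. The value is not yet known: "The thresholds will be provided after unblinding of the study". SAP 10.3.2 bases the basic counts on observed data and runs the inferential summary, a standardised logistic regression (SLR) with 95% CIs, on imputed data. For that purpose, "for subjects with imputed QOL-B Respiratory Symptoms score data, change from baseline values will be averaged across 50 available imputations"; PROMIS Fatigue averages are also rounded. The stated reason is consistency of data use with the anchor-based analysis. SAP 9.1.1 adds a p-value: "Nominal p-values will be provided for all efficacy analyses in which differences between groups and 95% CIs are evaluated".

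The PGI-S categorical analysis in SAP 11.2.2.1 follows the same rule: "imputations of change from baseline values will be averaged across 50 available imputations and rounded to the nearest integer". The proportion improved is then compared between arms "using Cochran-Mantel-Haenszel test stratified by history of MAC lung infection". No CI is planned there.

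Elsewhere the SAP keeps the imputations separate. Appendix I justifies their number by saying "Fifty replications are sufficient to reflect variability of the imputations". For the continuous PRO change, SAP 9.3.2.2.1 states: "The results of the analyses for each imputation will be combined using Rubin's rule". For binary culture conversion, which uses the same kind of SLR, Appendix I states: "The analysis as specified in Section 9.3.1.2 will be performed using each of the 50 full sets", followed by pooling with PROC MIANALYZE.

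**The concern.** Multiple imputation gives valid intervals because each completed data set carries residual variation and the spread between sets enters the standard error. Averaging first removes both. The mean of 50 draws is close to the subject's predicted value, so subjects with similar predictors fall on the same side of the threshold together. The single SLR then counts them as observed.

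Three consequences follow:

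- The reported SE is too small.
- The estimate itself is usually more variable than the pooled one, because a small shift in the fitted regression moves a whole group of imputed subjects across the cut.
- The proportion of responders among imputed subjects is wrong, so the arm difference can be biased in either direction, and can differ from zero under no effect when missingness differs by arm.

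At stake is whether a reported 95% CI and nominal p-value have roughly the properties their labels claim.

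**Working it through.** **The plan's own figure.** The documents give no coverage or error rate for these analyses. The nearest figure is the power of at least 80% for a 7-point converter difference (SAP 4.3.1), which also indicates a plausible SD.

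- Point-biserial r = 0.40 × φ(z)/√(pq), where p is the conversion rate, q = 1 − p and φ(z) is the normal density at the p-quantile. This gives 0.319, 0.315 and 0.303 at 50%, 60% and 70% conversion.
- Total SD = 7√(pq)/r = 11.0, 10.9 and 10.6. Within-group SD = total SD × √(1 − r²) = 10.4, 10.3 and 10.1.
- Power = Φ(7√(Npq)/SD − 1.96), with N = 100, 95 or 80, runs from 0.920 (50% conversion, none missing) to 0.813 (70%, 20% missing).

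The stated figure reproduces, and SD 11 is used below.

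**Why averaging misclassifies.** Assume R-squared 0.2 for the imputation model, arm means 10 and 5, threshold 8 and 20% missing.

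- Residual SD = 11√0.8 = 9.84. After averaging 50 draws it is 9.84/√50 = 1.39.
- SD of predicted values = 11√0.2 = 4.92, so averaged values have SD √(4.92² + 1.39²) = 5.11 instead of 11.
- True responder rates: Φ(2/11) = 57.2% and Φ(−3/11) = 39.3%, a difference of 18.0 points.
- Rates among averaged subjects: Φ(2/5.11) = 65.2% and Φ(−3/5.11) = 27.9%, a difference of 37.4 points.
- Expected estimate: 0.8 × 18.0 + 0.2 × 37.4 = 21.8 points.

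With means 4 and 0 and threshold 14, the true difference is 8.0 and the difference among averaged subjects is 2.2. The estimate becomes 0.8 × 8.0 + 0.2 × 2.2 = 6.9 points, biased towards zero.

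With no effect (both means 7), threshold 12 and 10% vs 30% missing, the true rate is 32.5% and the averaged rate 16.4%. The spurious difference is 0.2 × (32.5 − 16.4) = 3.2 points. These hand figures ignore error in estimating the regression.

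**Simulation, WSMC.** 50 per arm, SD 11, data missing completely at random, 50 normal-regression imputations within arm on baseline score and MAC history (30% subsequent), SLR with delta-method SE, 3,000 trials per scenario. Ranges cover six mean/threshold positions at R-squared 0.2.

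| Missing | Average, then classify | Classify, then pool |
|---|---|---|
| 5% | 93-94% | 94-96% |
| 10% | 90-94% | 94-96% |
| 20% | 85-92% | 94-96% |

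- Complete data cover 94-95%. At 20% missing, averaging covers 78-92% at R-squared 0.05 and 90-92% at 0.5.
- Means 10 vs 5, threshold 8, 20% missing: averaging reports SE 9.6 points against a true SD of 12.4; pooling reports 10.6 against 10.4. Giving the averaged estimate the pooled SE lifts coverage only from 85% to 89%, so most of the loss is extra variance and bias.
- Bias at 20% missing: 21.7 against a true 18.0 points; 7.1 against 8.0 when both means lie far on one side of the threshold.
- No effect, 10% vs 30% missing, threshold 2 or 12: spurious differences of 2.5-3.0 points, the sign depending on arm and threshold. With 5% vs 20% missing, about 2 points. Pooling stays within 0.7 points of truth in all scenarios.
- No effect, equal missingness, threshold 8: nominal p is below 0.05 in 6.9% of trials at 5% missing and 13.6% at 20% (pooled 5.3% and 4.6%).

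**Variants.** Re-estimating the threshold in each trial from an anchor group: averaging covers 91-93% at 5% missing and 86-88% at 20%; pooling 93-96%. Imputing intercurrent-event (ICE) subjects from retrievers, with 8%, 12% and 19% missing in total: averaging 91-94%, 90-94% and 88-92%; pooling 95-97%. A separate simulation with SD 15, means 8 vs 4 and threshold 6 gave 92.7%, 90.7% and 83.8% for averaging at 5%, 10% and 20% missing.

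**Simulation, PGI-S.** Under no effect, 12 settings of 4,000 trials at each missing rate: the CMH test rejects at nominal 5% in 5.3-6.9%, 6.0-8.4% and 8.2-13.0% of trials at 5%, 10% and 20% missing, against 4.5-5.9% with complete data. In an illustrative setting, subjects with missing data are coded improved/no change/worse in 33/60/7% when the truth is 40/41/19%; rounding within each imputation gives 41/37/22%.

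**The case against.** The strongest reply has four parts.

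- **Status.** SAP 7.2 calls every CI and p-value nominal, with no inference intended. WSMC is exploratory and goes in the CSR appendix, observed-data counts are also reported, and the PGI-S change score has a further analysis modelled on the QOL-B one, which pools. All this stands, and it is why the point is minor. It does not excuse an interval labelled 95% that covers less, nor a biased point estimate.
- **Unknown size.** The documents give no threshold, no imputation R-squared and no expected Month 7 missing rate; 0-30% appears only as a set of planning conditions. Retrieved assessments are used and subjects who stop study drug are encouraged to stay, so 20% may be pessimistic. At 5% missing the loss is slight, and the PGI-S rejection range overlaps that for complete data. The SD is also open to reading: if the planned contrast is 7 points in converters against 3 in non-converters, the implied SD is about 6.
- **Stated reason.** Averaging is meant to match the anchor-based analysis in the Validation Analysis Plan, which is not available here, so that reason cannot be fully assessed. But a fixed threshold can be applied within each imputed set, and the averaged display can be kept beside the pooled result.
- **Wording.** A PGI-S p-value that is too small describes rejection rates under no effect. In a single data set with a real effect, averaging can also make p larger. That qualification is correct.

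**Conclusion.** The concern holds and is minor. As written, the WSMC interval omits between-imputation variance and rests on an estimate that is usually more variable than the pooled one and can be biased either way. The exception on variability is a threshold far from both means with R-squared 0.05 or 0.2. The PGI-S test rejects too often under no effect, and its category proportions are distorted. The shortfall is slight at 5% missing and clear at 20%.

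The direction follows from the SAP text alone. The size rests on assumed thresholds, R-squared and missing rates, on SD 11, and mainly on data missing completely at random. Deaths, the ELC fallback reference group and outcome-dependent missingness were not modelled. No confirmatory conclusion is affected.

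**What to change.** - **SAP 10.3.2:** apply the threshold within each of the 50 imputed sets, with any PROMIS rounding done within each set. Run the SLR on each set and combine by Rubin's rule with PROC MIANALYZE, as Appendix I does for culture conversion.
- **SAP 11.2.2.1:** assign the PGI-S category within each imputed set by a stated rule, for example nearest integer limited to −4 to 4. Then pool the proportions and a risk difference stratified by MAC history. If the CMH test is kept, combine it across sets after a Wilson-Hilferty transformation.
- Keep the averaged version, if wanted, as a labelled supplementary display, and state that the CI treats the WSMC threshold as known.

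The cost is SAP wording and minor programming. Averaging already requires 50 imputations on whichever scale is used, so no extra imputation is needed. At R-squared 0.2, WSMC intervals become about 2-5% wider at 5% missing and 11-21% wider at 20%. The pooled PGI-S test is slightly conservative at 20% missing, rejecting in 3.4-5.0% of null trials.

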## 10.4. Actigraphy

### 10.4.1. Variable Description

The Philips Actiwatch Spectrum PRO actigraphy device resembles a wristwatch and senses the activity of the wearer. It is to be worn continuously by the subject throughout the duration of the study. It is water-resistant and does not need to be removed for bathing. The data collected should be downloaded at each in-clinic visit or during a home care visit (if applicable).

The data are collected continuously by the device and processed by Philips proprietary validated algorithms to derive daily values. Data are collected from visit Day 1 until EOS.

The following variables will be summarized by week using descriptive statistics:

- Total activity count
- Maximal activity count
- Daily percent of mobile time (%)
- Total night sleeping time, TNST (minutes)
- Sleep efficiency (%)  
*Sleep efficiency is defined as the ratio of TNST and time in bed.*
- Duration nocturnal sleep bouts, DNSB (minutes)  
*Average duration of nocturnal sleeping bouts during time in bed. A higher DNSB indicates longer sleeping bouts and, in turn, less nocturnal sleeping disturbances.*
- Wake after sleep onset, WASO (minutes)  
*Time spent awake during time in bed after the first nocturnal sleep onset.*
- Total day sleeping time, TDST (minutes)
- Number of daytime sleep bouts, NDSB  
*Number of daytime sleeping bouts indicates how many naps a patient takes during the day.*
- Duration daytime sleep bouts, DDSB (minutes)  
*Average duration of daytime sleeping bouts during the day. A higher DDSB indicates longer naps.*
- Fragmentation index (%)  
*An index of restlessness throughout the rest period. It is the sum of percent mobile and percent one-minute immobile bouts for the given interval.*

For each of the variables above weekly scores will be computed. A weekly score is computed for a subject if at least 4 daily scores are available for a week.

#### 10.4.2. Analysis

Descriptive summary for the activity and sleep variables will be performed for each week per treatment group. The following will be presented from baseline to Month 7:

- The number and percentage of subjects with data recorded.
- Descriptive statistics (mean, median, standard deviation, first and third quartiles, skewness, minimum and maximum).

- Descriptive statistics for change from baseline to each post-baseline week. The denominator is the number of subjects in the study in the corresponding week.
- A graphical representation will be also provided as timeseries showing weekly mean and weekly mean change from baseline (across patients).

## 10.5. Subgroup Analysis

Subgroup analyses will be performed on the following:

1. QOL-B non-respiratory symptoms Month 7
2. Subjects meeting WSMC QOL-B Month 7
3. Subjects meeting WSMC PROMIS Fatigue Month 7

Subgroup factors are shown in the list below:

- Age: < 65 years,  $\geq$  65 years
- Gender: Female, Male
- Race: American Indian or Alaska Native, Asian, Black or African American, Native Hawaiian or Other Pacific Islander, White (races with small counts might be excluded from summaries)
- Stratification variable 'History of MAC lung infection': initial, subsequent
- Stratification variable 'Region': North America, Europe, and Rest of World
- MAC infection at baseline: Mycobacteria isolate species (*Mycobacterium avium* complex overall, *M. avium*, *M. intracellulare*), and other speciated and unspciated MAC)

Subgroup analysis will use the same analytical approach as the main analysis. Statistical modeling will not include history of MAC lung infection as covariate.

